13.0 Statistical Considerations

13.1Study Design

Our target sample size for this study will be 200 caregiver-patient dyads (after 20% attrition). The planned sample size is 100 caregiver-patient dyads per treatment group. The power of statistical tests (two-sided 0.05 level of significance) is shown below for the primary outcomes of each specific aim. The effect sizes are shown as pairs of numbers representing the expected control group mean, based on published data, and the hypothetical population mean for the intervention care group. The SD column is based on published data, and power is conservatively estimated for a simple t-test on a single post-intervention measurement. The planned analysis, described in section E.5, will adjust for baseline values, and will combine longitudinal assessments, both of which will improve power.

A total of 80 new cases of stage I-III surgically treated NSCLC were available at City of Hope in fiscal year 2015. Our institutional race distribution is 56.2% Caucasian, 20.5% Hispanic, 4.7% Black, 13.5% Asian, and 5.1% other (38.7% ethnic minorities overall). These statistics should reflect the anticipated race distribution for participants. All efforts will be made to accrue minorities. Our pilot study demonstrates that we are able to accrue minorities (38%) to match the population at City of Hope.

A sample size of 100 per arm was calculated, based primarily on outcome means and variation observed in our previous studies (see Section E.1 for sample size calculations and power analysis). We have projected attrition based on previous studies. We will enroll 100 participants per arm to allow for 20% drop-out/attrition during the course of the study. We will enroll a total of 200 dyads in order to retain 160 dyads at 3-months. With a 52 month accrual plan, we estimate that 4 caregiver-patient dyads will need to be accrued per month. With a total pool of 80 potential dyads per year, this yields approximately 7 dyads per month that are eligible for the study. Hence, we will have a sufficient pool of eligible participants for study accrual. In our lung cancer Program Project (N=366), we were able to enroll 4 FCGs and patients per month. ^{59, 114}

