We will study FCGs and patients age 21 and over to obtain participants across a spectrum of chronological ages. A range of ages is expected although we anticipate at least 68% of NSCLC patients will be \geq 65 years. We anticipate that the majority of FCGs will be spouses and \geq 60 years old given the patient age distribution. Based on our experiences, 90% of patients have an identified FCG. We acknowledge that the aging spectrum is heterogeneous and that older patients have a higher risk of surgical morbidity. We anticipate that the majority of FCGs will be female (75%), but expect an equal representation by sex for patients. We recognize that age and sex are important influencing factors. We will examine the moderating effect of these biological variables on outcomes in Exploratory Aim 1.

IRB 17238 02/02/2023

Specific Aim 1 addresses the effects of the MSM Intervention on FCG outcomes, and **Table 3** provides FCG outcome effect size and power based on 80 participants per group. **Hypothesis 1.1** will address FCGs' psychological distress and burden. The study by Zwahlen et

Table 3. FCG Outcomes Effect Size and Power

Outcome	Measure	Effect	SD	Power
H1.1 Psychological distress	Distress thermometer	3.7 v 2.5	2.6	83%
H1.1 Caregiver burden	Objective burden score	22.0 v 20.2	4.0	81%
H1.2 Caregiver preparedness	Preparedness score	3.7 v 4.1	0.72	93%
H1.2 Caregiver QOL	Total QOL score	5.9 v 6.6	1.42	87%
H1.3 Social work referrals	FCG healthcare use	20% v 40%	NA	80%
H1.3 FCG center resource use	FCG healthcare use	30% v 60%	NA	97%

al⁷¹ provides distress thermometer (DT) scores for 306 family members, including 32 relatives of lung cancer patients. The mean score was 3.7, and the standard deviation was 2.6. With this SD, a reduction of the mean by 1.2 points could be detected

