Data management is of key importance in this study. Our institutional research informatics core will develop an electronic data entry, capture, and storage system that will perform tracking functions (accrual, enrollment, consenting, data collection, and intervention delivery). We will develop a query system to address data validity and integrity by making early identification of cases of recruitment irregularity, data collection inconsistency, data inaccuracy or incompleteness. Data will be audited for accuracy prior to scoring and analysis.

Our primary data analysis will be according to intention-to-treat, i.e. all participants will be included in the analysis whether or not they received all prescribed intervention components. Participants who are lost to follow-up due to mortality will not be included. Reasons for study dropout will be recorded. Participants with missing items will be compared with those having non-missing items to determine whether missing data are random or can be accounted for by other variables. Broadly, our data may be missing at random (MAR) or missing not at random (MNAR). Generalized linear model with robust (sandwich) variance estimator model will be fitted to the data, with time, baseline, treatment arms, and interaction of time and treatment as explanatory variables. This approach provides valid standard errors with repeated measurement of individuals. It also accommodates missing time points by using the model of time effects to reduce bias. For MNAR, a pattern mixture model⁵⁵ will be fitted to the data to correct for informative drop-out. In particular, three patterns will be defined: a pattern consisting of participants who died during the study period, a pattern of participants with relapse, and a pattern of participants who remained disease free. Within each pattern, data will be modeled by the random effects model. To compare treatment arms, the effects of both arms will be respectively estimated using a weighted average across all patterns weighted by their sample proportions.

IRB 17238 02/02/2023

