These two hypotheses will be tested in the same way. We will address the effect of the intervention on FCG psychological distress, burden, preparedness for caregiving, and QOL at months 1 and 3, adjusted for baseline response. Scores for all outcome measures will initially be summarized graphically and numerically at baseline, month 1, and month 3, for each stratum, along with simple diagnostic plots. The need for transformation will be accessed. A generalized linear mixed model will be fit to estimate the distribution of 1 month and 3 month score as a function of treatment, stratum, occasion (month 1 or 3) and baseline value. The robust (sandwich) variance estimator will be used to accommodate the correlation of the two occasions, and the estimated treatment effect for the adjusted average of the 1 and 3 month outcomes will be estimated and tested, in order to limit multiplicity with respect to occasions, and to improve upon the designed power by combining information, effectively reducing standard deviations relative to those used for planning. This is similar to the analysis of average outcome for the two post-treatment occasions, except that it accommodates missing outcome evaluations by attributing observations to the appropriate occasion (comparing like with like), and avoids overstating information. Analysis of average outcome does provide a convenient robustness check. Each analysis will be a repeated measures ANCOVA statistical design, removing variances prior to examining mean squares for the group by occasion interactions, and covarying the baseline scores. The independent variable will be group (intervention vs. attention control). Hypothesis 1.3: The intervention group will have higher social work referrals and family resource center use.

FCG cancer support services will be evaluated by recording social work referrals and family resource center use. Each subject will be classified as having an event or not. There is no baseline value, but the data will be tabulated by surgery stratum, and tested for homogeneity (interaction) before estimating and testing the overall treatment effect.

IRB 17238 02/02/2023

Specific Aim 2: Test the effects of the MSM Intervention on patient outcomes and healthcare resource use at discharge and 3-months post-discharge, comparing intervention and attention control groups.

Hypothesis 2.1: The intervention group will experience lower psychological distress and higher OOL.

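### The missing-data model is named three ways and never fully specified; fitted under working independence, as the text allows, it is not in general unbiased under MAR dropout

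*Combined protocol and SAP*

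**What the plan says.** Three descriptions of the primary analysis of the quantitative outcomes stand in Section 13.1 and its subsections.

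- **Missing-data paragraph (Section 13.1).** Having said that data may be MAR or MNAR, the plan states: "Generalized linear model with robust (sandwich) variance estimator model will be fitted to the data". The terms are time, baseline, arm and time by arm. Of missing visits it says: "It also accommodates missing time points by using the model of time effects to reduce bias". Random effects appear in this paragraph only inside the pattern mixture model reserved for MNAR.
- **Section E.5, Specific Aim 1.** A generalized linear mixed model is named for the 1-month and 3-month scores, with treatment, stratum, occasion and baseline. No random effect, covariance structure or estimation method follows. Instead: "The robust (sandwich) variance estimator will be used to accommodate the correlation of the two occasions". The tested quantity is the adjusted average of the two months.
- **End of the same paragraph.** Each analysis is also called a repeated measures ANCOVA based on mean squares.

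Specific Aims 2 and 3 reuse the Aim 1 plan. Discharge scores are collected (Table 2 in Section 12.1.3), and Section 2.2 makes discharge a primary time point, but the E.5 model leaves them out.

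**The concern.** The sandwich repairs the standard error when correlation has been ignored in estimation; it leaves the point estimate as it was. Time effects make sure that 3-month scores are compared with 3-month scores. They do not let a person's observed 1-month score inform that person's missing 3-month score. Under working independence the people who stay stand in for those who left, given only baseline, arm and time. MAR is wider than that: it also covers dropout that follows earlier post-baseline scores, and there the estimate is not in general consistent.

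The plan expects 20% attrition, and the MSM and control contacts differ in content (nurse coaching against calls about general materials). Arm-specific dropout is therefore possible, and it would touch every quantitative primary outcome. The three labels also treat missing visits differently, so analysts following the same text could report different effects.

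**Working it through.** **Inputs from the documents.** Test: "two-sided 0.05 level of significance". Table 3 "provides FCG outcome effect size and power based on 80 participants per group". Attrition: "We will enroll 100 participants per arm to allow for 20% drop-out/attrition during the course of the study", and "We will enroll a total of 200 dyads in order to retain 160 dyads at 3-months". Caregiver distress thermometer: "The mean score was 3.7, and the standard deviation was 2.6", with a planned reduction of 1.2 points.

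**The plan's own figure.** SE of the difference = 2.6 × √(2/80) = 0.411. Then 1.2/0.411 = 2.92, 2.92 − 1.96 = 0.96, and Φ(0.96) = 83%, as Table 3 states. Attrition agrees: 100 × 0.80 = 80. The planned effect is 1.2/2.6 = 0.46 SD.

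**Assumptions (not in the documents).** Equal correlation ρ between all visits, 0.5 to 0.7. Dropout of 20% overall, with log-odds of 1 per SD of the driving score.

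**Hand check, control-only dependence on the month-1 score.** With this dropout, completers' mean month-1 score is about 0.17 SD below that of the whole arm.

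- Without baseline in the model, the 3-month bias would be about 0.17ρ: 0.085 SD at ρ = 0.5 and 0.119 SD at ρ = 0.7.
- With baseline in the model, as planned, the selection left over is 0.17(1 − ρ²) and the slope of month 3 on month 1 given baseline is ρ/(1 + ρ). The product is 0.17ρ(1 − ρ): 0.043 SD at 0.5 and 0.036 SD at 0.7. Against 0.46 SD that is about 9% and 8%.

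**Simulation, baseline in the model, dropout following the month-1 score, ρ = 0.5 to 0.7.**

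| Dropout pattern | 3-month bias | Share of planned effect | Average of months 1 and 3 |
|---|---|---|---|
| Same dependence, 20% in each arm | none | 0% | 0% |
| Same dependence, 15% v 25% | about 0.02 SD | 4–5% | about 2% |
| Control arm only, 20% in each arm | about 0.04–0.045 SD | 8–10% | 4–5% |
| Opposite directions, 20% in each arm | about 0.08–0.09 SD | 16–20% | 8–10% |

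A likelihood fit with unstructured covariance showed no bias beyond simulation error in any row. The sign depends on who leaves: losing worse-off controls shrinks the estimated benefit, and losing worse-off MSM participants inflates it.

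**Dropout after discharge as well** (driven by the last observed post-baseline score, ρ = 0.3 to 0.7, in points on the distress thermometer).

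| Pattern | GLM, 3 months | GLM, average of 1 and 3 | Likelihood on months 1 and 3 only, average | Likelihood on all visits, average |
|---|---|---|---|---|
| Control only | 0.11–0.12 | 0.08–0.10 | 0.05–0.07 | within about 0.01 |
| Opposite directions | 0.21–0.25 | 0.16–0.19 | 0.11–0.12 | within about 0.01 |

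As shares of 1.2 points, the GLM 3-month figures are 9–10% and about 17–21%; for the average they are about 7–8% and 13–16%. A likelihood model without discharge removes only about a third of the bias. When dropout followed baseline alone, every model was within 0.01.

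**Consequence if the bias acts against the intervention**, on the plan's t-test basis: an effect of 1.09 gives 1.09/0.411 − 1.96 = 0.69, power about 76%; an effect of 0.95 gives 0.95/0.411 − 1.96 = 0.35, power about 64%.

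**The case against.** The strongest reply is that E.5 already names a mixed model for the hypotheses that matter, and that adding a sandwich variance to a mixed model does not remove its likelihood estimation. Working independence is an inference; no sentence states it. The plan claims only to reduce bias, adds a pattern mixture model for MNAR, and will compare participants with and without missing items. This stands to the extent that nobody can say the plan commits to an independence GLM. It does not settle the matter, because the missing-data paragraph names a GLM, and E.5 leaves the correlation to the sandwich and states no structure.

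A second reply is that nothing in the documents shows arm-specific, score-driven dropout. That is correct. The pilot lost 7 of 29 caregivers (7 + 22 completers, 24%), but Section 2.4 does not split this by arm or relate it to scores, and follow-up was 2 to 4 weeks. Controls also receive the same number of calls and the same assessments.

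Four stronger readings are tempting, and none is supported:

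- That the GLM is biased under MAR as such. It is not when missingness depends only on baseline, arm and time, and the contrast is not when dropout works identically in both arms.
- That control-only dependence costs about a fifth to a quarter of the effect. That size arises only if baseline is left out (0.085/0.46 = 18%, 0.119/0.46 = 26%), and the plan includes it.
- That the ANCOVA label means complete cases. Mean-squares methods ordinarily need them, but the same paragraph says missing evaluations will be accommodated.
- That any likelihood mixed model on the planned data would cure the problem. It needs a suitable covariance structure, and it needs the discharge score if dropout follows that score.

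**Conclusion.** The concern holds as a specification gap with a conditional bias. The documents permit an estimator that is not in general consistent under MAR, and they describe the primary analysis in three ways that do not agree. Bias requires dropout that follows post-baseline scores, together with a difference between arms in that dependence or in the rate. Where both hold, the 3-month bias is modest in the milder cases (4% to 10% of the planned effect) and reaches 16% to 21% only with opposite dependence by arm. The average of months 1 and 3, which E.5 tests, carries about half as much, or more if people also leave after discharge. These sizes rest on assumed correlations and dropout strength, for which the documents give no figures. The change is worth making because it costs almost nothing and also settles which model is primary.

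**What to change.** Reconcile the missing-data paragraph of Section 13.1 with Section E.5 by naming one primary model for the quantitative outcomes: a mixed model for repeated measures fitted by REML, with discharge, 1-month and 3-month scores as responses; treatment by time, baseline by time and randomisation stratum as fixed effects; and an unstructured within-person covariance. Take the planned contrasts (discharge, 3 months, average of 1 and 3 months) from that model. Keep the GLM with sandwich variance and the ANCOVA as labelled sensitivity analyses, and the pattern mixture model for MNAR.

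The cost is SAP wording and standard software. The discharge scores are already collected, so no new data, visits or participants are needed.

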Clinical Observations and Tests to be Performed:

Disease and surgical characteristics: date of diagnosis, pre-operative risk factors, pre-operative treatments, pre-operative pulmonary function tests, date of surgery, type of surgical procedures, admission date and status, clinical staging, postoperative events/complications, discharge date and status, discharge disposition, pathological staging, and smoking cessation plans, postoperative urgent care/ER visits, and 30 and 90-day hospital readmissions. Geriatric assessment for FCGs (baseline, 3 months) and patients (baseline, first postoperative clinic visit, and 3 months).

Statistical Considerations:

In Aims 1, 2, and 3, outcomes and mediators will be examined across 3 time points (discharge, 1 and 3 months post-discharge) by treatment group using baseline as covariates. We will also test intervention effects on FCG cancer support services use and patient healthcare resource use. The primary outcome is the change in scores from baseline to discharge (immediate effect) and 3 months post-discharge (sustained effect). In EA 1, we will explore moderators and reciprocal relationships. In EA 2, we will qualitatively explore participants' experience with the MSM Intervention.

Sponsor/Licensee:

National Cancer Institute

Case Report Forms

Not Applicable

IRB 17238 02/02/2023

Table of Contents

SECT	ION	•••••	PAGI	E
Experin	nental D	esign S	chema	2
Protoco	l Synop	sis		3
Table o	f Conter	nts		5
Abbreiv	viations.			8
1.0	Goals a	nd Obje	ectives (Scientific Aims)	0
2.0	Backgr	ound	1	1
	2.1	Introdu	action/Rationale for Development1	1
	2.2	Overvi	ew of Proposed Study1	4
	2.3	Preclin	ical Studies1	4
	2.4	Human	Studies1	4
3.0	Patient	Eligibil	ity1	5
	3.1	Inclusion	on Criteria1	5
		3.1.1	Disease Status	6
		3.1.2	Age Criteria, Performance Status and Life Expectancy	6
		3.1.3	Child Bearing Potential	6
		3.1.4	Protocol-Specific Criteria	6
		3.1.5	Informed Consent/Assent	6
		3.1.6	Prior Therapy1	6
	3.2	Exclusi	ion Criteria	6
		3.2.1	Study-Specific Exclusions	6
		3.2.2	Non-Compliance 1	7
	3.3	Inclusion	on of Women and Minorities1	7
4.0	Screeni	ng and l	Registration Procedures1	7
	4.1	_	ing Procedures	
	4.2	Inform	ed Consent	7
	4.3		ration Requirements/Process	
	4.4	_	mization and/or Dose Level Assignment1	
5.0	Treatme	ent Prog	gram	8
	5.1	_	ntion Overview1	
	5.2		d Duration of Therapy2	
			••	

	5.3	Criteria for Removal from Treatment	22
	5.4	Subject Follow-Up	23

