2.2 Overview of Proposed Study

This prospective, longitudinal, mixed-methods RCT is designed to test the efficacy of the MSM Intervention in lung cancer surgery. In Aims 1, 2, and 3, outcomes and mediators will be examined across 3 time points (discharge, 1 and 3 months post-discharge) by treatment group using baseline as covariates We will also test intervention effects on FCG cancer support services use and patient healthcare resource use. The primary outcome is the change in scores from baseline to discharge (immediate effect) and 3 months post-discharge (sustained effect). In EA 1, we will explore moderators and reciprocal relationships. In EA 2, we will qualitatively explore participants' experience with the MSM Intervention.

This study will be conducted in compliance with the protocol, Good Clinical Practice (GCP) and the applicable regulatory requirements.

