12.1.2 Subject Consent Form

Initial verbal consenting will only be used when potential participants are not in the clinic. In these situations, the Research Nurse and CRA will use the approved information sheet (available in both English and Chinese) for verbal consent process. An informed consent (available in both English and Chinese) will then be obtained either in writing in person, by mail, or electronic mail, or electronically via other electronic applications (i.e. DocuSignTM). Otherwise, all participants will complete either a written or electronic informed consent (i.e. DocuSignTM) prior to study participation. The study will use one written or electronic informed consent (with signature line) and one information sheet (without signature line) for FCGs, and one written or electronic informed consent (with signature line) and one information sheet (without signature line) for patients. Documentation of initial verbal consent for study participation will be charted through progress notes and maintained in the patients' electronic medical records as required by the Institutional Review Board.

12.1.3 Data Collection Forms and Submission Schedule

Table 2 provides outcome measures and the corresponding evaluation time points. All outcome measures completed by patients/FCGs are available and validated in both English and Chinese. We will collect sociodemographic and health status data (e.g. age, sex, race/ethnicity, education, employment, relationship to patient, religious preference, marital status, living

IRB 17238 02/02/2023

situation, income, co-morbidities, and tobacco history) for both FCGs and patients at baseline. Outcomes are assessed at baseline (before surgery), discharge, 1 month, and 3-months post-discharge. They will take about 30 to 45 minutes to complete. Outcomes were selected based on our conceptual model, previous research in lung cancer, and recommendations on common data elements for self-management research.⁹⁷

Table 2. Outcome Measures by Aims and Assessment Time Points								
	Measures	Baseline	Discharge	1 month	3 months			
	Distress Thermometer	X	X	x	х			
Family	Montgomery Borgatta Caregiver Burden Scale	х	Х	х	х			
Caregivers	Preparedness for Caregiving Scale	х	X	x	х			
Ü	COH-QOL-Family	х	X	х	х			
	Family Caregiver Healthcare Use Survey		X	х	х			
	Distress Thermometer	X	X	x	х			
Patients	FACT-L	X	Х	х	х			
	Patient Healthcare Use Survey (non-COH)			x	х			
	Medical Chart Audit Form				x			

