- **E.4. Preliminary Analysis** Initially, standard data descriptions, along with q-q plots and similar diagnostics will be used to check each outcome measure prior to analyses addressing hypotheses. Transformations will be considered, if necessary, to improve symmetry, variance homogeneity, and distribution, and to accommodate floor and ceiling effects. For several outcomes with high coefficient of variation, we anticipate using analysis on a logarithmic scale, potentially permitting presentation of geometric means and multiplicative effects.
- E.5. Statistical Methods by Study Aims Our general approach is to produce a confidence interval and corresponding hypothesis test for the effect of treatment (as intended) on each outcome, with the stratum used in randomization, and the baseline value of the outcome of interest included as covariables (i.e. analysis of covariance). This approach reduces residual variance and improves power, and randomization removes potential bias due to baseline differences. For the sake of robustness, secondary analyses will include a simple comparison without covariables, as well as a three-covariable model that includes a propensity score to address any residual imbalance in medical or socio-demographic variables. This approach generally minimizes the missing data problem for the primary analysis. Multiplicity: Planning is based on significance levels of 0.05, as each primary outcome is well-motivated a priori, and the merits of the intervention are expected to be seen in multiple outcomes. Statistically significant change in a single outcome, as would be controlled by family-wise adjustment procedures, would not be enough to motivate continued pursuit of the intervention. Two-sided significance levels are quoted. All of the hypotheses are also dividing hypotheses in the sense of Cox¹¹⁶ so both the a priori direction, and the decision argument of Lehman¹¹⁷ justify two-sided tests.

Specific Aim 1: Test the effects of the MSM Intervention on FCG outcomes and cancer support services use at discharge and 3-months post-discharge, comparing intervention and attention control groups. **Hypothesis 1.1:** The intervention group will experience lower psychological distress and caregiver burden. **Hypothesis 1.2:** The intervention group will experience higher caregiving preparedness and QOL.

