For this hypothesis, we will address patient psychological distress and QOL. Distress and QOL are each quantitative scales measured at both 1 month and 3 months. These will be analyzed by the same plan described for Specific Aim 1, hypothesis 1.1 and 1.2. Each analysis will be a repeated measures ANCOVA statistical design, removing variances prior to examining mean squares for the group by occasion interactions, and covarying the baseline scores. The independent variable will be group (intervention vs. attention control).

Hypothesis 2.2: The intervention group will have lower in-home nursing care, lower urgent care/ER visits, and lower hospital readmissions.

Similar to Specific Aim 1, hypothesis 1.3, patient healthcare resource use will be evaluated by recording in-home nursing care, urgent caregcp/ER visits, and readmissions (COH and non-COH encounters). Each subject will be classified as having an event or not. There is no baseline value, but the data will be tabulated by surgery stratum, and tested for homogeneity (interaction) before estimating and testing overall treatment effect.

Specific Aim 3: Test the effects of the MSM Intervention on outcome mediators at discharge and 3-months post-discharge, comparing intervention and attention control groups. **Hypothesis 3.1:** FCGs and patients in the intervention group will experience higher activation, self-efficacy, and knowledge.

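### For the score outcomes, Section E.5 tests the average of months 1 and 3 and names no discharge or 3-month contrast, although those two are the declared primary effects

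*Combined protocol and SAP*

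**What the plan says.** **Declared effects.** In the Synopsis (Statistical Considerations) and again in Section 2.2, the primary outcome "is the change in scores from baseline to discharge (immediate effect) and 3 months post-discharge (sustained effect"). Section 2.2 adds that "outcomes and mediators will be examined across 3 time points (discharge, 1 and 3 months post-discharge) by treatment group". The aims, in Section 1.0 and in the aim headings inside E.5, place the tests "at discharge and 3-months post-discharge, comparing intervention and attention control groups". Section 12.1.3 confirms that the data exist: "Outcomes are assessed at baseline (before surgery), discharge, 1 month" and 3 months, and Table 2 marks every score outcome at discharge.

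**Planned test.** For H1.1 and H1.2, E.5 summarises baseline, month 1 and month 3. It fits a model whose occasion factor has the levels month 1 and month 3, and "the estimated treatment effect for the adjusted average of the 1 and 3 month outcomes will be estimated and tested". The stated reasons are to limit multiplicity over occasions and to gain power. H2.1 takes over the plan with the remark that "Distress and QOL are each quantitative scales measured at both 1 month and 3 months"; H3.1 does likewise. Each of these paragraphs also describes a repeated measures ANCOVA, "removing variances prior to examining mean squares for the group by occasion interactions, and covarying the baseline scores".

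**Elsewhere in Section 13.1.** The general model is fitted "with time, baseline, treatment arms, and interaction of time and treatment as explanatory variables", but its occasions are not listed and no contrast is named. Exploratory Aim 1 takes score outcomes at discharge and 3 months. The mediation models under H3.1 use month 1.

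**The concern.** Averaging post-treatment visits is a legitimate choice. Here, however, the average estimates a different effect from the declared one: discharge, half of the declared primary outcome, is left out, and month 1, which is not a declared primary time point, is put in. The same pattern runs through the summaries, the model and the test for three aims, so it is not a slip in one sentence.

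The gap is wider for discharge, which is absent from the E.5 model, than for 3 months, which is in the model but merged with month 1. In neither case does E.5 name a test. An analyst who wants the immediate or sustained effect would have to settle the contrast, and for discharge the occasions in the model, after the fact. Meanwhile the specified test can miss a declared effect that exists, or be significant when neither exists.

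The role of the group-by-occasion interaction is also unstated. With baseline as a covariate and months 1 and 3 as occasions, it compares the effect at month 1 with the effect at month 3. It does not test whether the intervention works.

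**Working it through.** **Inputs.** From Section 13.1 and Tables 3 and 4: two-sided alpha 0.05; 80 per group; caregiver distress 1.2 points, SD 2.6; objective burden 1.8, SD 4.0; FACT-L 7.6 (101.3 − 93.7), SD 17.0. *Assumed:* correlation ρ between month 1 and month 3 scores of 0.3, 0.5 or 0.7. The documents give neither ρ nor a trajectory of effect over visits, so the patterns below are illustrations. Baseline adjustment is ignored except where stated.

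**Step 1: the plan's own figure.** Noncentrality = δ / (SD·√(2/n)) = 1.2 / (2.6 × √(2/80)) = 2.92 on 158 df. Power is 82.7%, against the stated 83%. This is a single-visit calculation, so it matches a discharge or 3-month contrast and not the average.

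**Step 2: SD of the two-visit average** = SD·√((1+ρ)/2). For caregiver distress: 2.6 × √0.65 = 2.10, 2.6 × √0.75 = 2.25, 2.6 × √0.85 = 2.40.

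**Step 3: power of the E.5 test, caregiver distress.** The average estimates (effect at month 1 + effect at month 3) / 2.

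| Where the 1.2-point benefit lies | What the average estimates | ρ 0.3 | ρ 0.5 | ρ 0.7 |
|---|---|---|---|---|
| All visits | 1.2 | 94.9% | 91.8% | 88.2% |
| Month 3 in full, half at month 1 | 0.9 | 77.0% | 71.0% | 65.5% |
| Month 3 only | 0.6 | 43.6% | 38.8% | 35.0% |
| Month 1 only (both declared effects zero) | 0.6 | 43.6% | 38.8% | 35.0% |
| Discharge only | 0 | 5% | 5% | 5% |

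The last row does not depend on ρ, because discharge scores are not in the model. In the month-1-only case the average is significant in 34-42% of trials for objective burden and 33-41% for FACT-L.

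**Step 4: the interaction.** Under a constant benefit the difference between the month 1 and month 3 effects is zero, so its test rejects at about the nominal rate: 4.9% in 20,000 simulated trials at ρ = 0.5.

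**Step 5: price of two contrasts.** Testing discharge and 3 months each at 0.05 gives a chance of at least one false positive per outcome of 9.5%, 9.1% and 8.3% for correlations 0.3, 0.5 and 0.7 between the two (bivariate normal). At 0.025, the first Holm step, power for caregiver distress is 74%. With an assumed baseline correlation of 0.5 the SD falls by √(1 − 0.25) and power is 86%. Without baseline adjustment, the same step gives 72% for burden, 71% for FACT-L, 74% for patient distress and 71% for activation.

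**The case against.** The best defence is that the combined test is deliberate. Section 13.1 says in its sample size text that longitudinal assessments will be combined to raise power, and E.5 gives its reasons. Under a constant benefit the average does beat the single-visit test. That stands, and it means the mismatch could equally be cured by correcting the declaration. It does not explain why discharge is dropped while the aims still name it.

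Second, the general time-by-treatment model, read with the three time points in Section 2.2, could produce both declared effects. It could, but it names neither occasions nor contrast, and the aim-specific text restricts the occasions to months 1 and 3.

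Third, all-or-nothing trajectories are extreme. This is fair: with the full effect at month 3 and half at month 1, power is 66-77%; with three quarters at month 1 (average effect 0.875 × 1.2 = 1.05) it is 79-88%, about level with the single-visit 83%. The loss for a sustained effect may therefore be small. For an effect at discharge only, it is total. The 5% rejection rate for the interaction holds by construction and matters only if someone reads that term as the hypothesis test.

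Fourth, the yes/no outcomes (H1.3, H2.2) have no stated time point either. That is a separate matter; they are not averaged, and this point is limited to scores.

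**Conclusion.** The concern holds and must be fixed. For H1.1, H1.2, H2.1 and H3.1, the only treatment effect that E.5 says it will estimate and test is not the declared primary effect. This rests on the text alone. The power figures show the consequence under an assumed ρ of 0.3 to 0.7 and illustrative trajectories. For caregiver distress they range from a gain (88-95% against 83%) if the benefit is constant, through a loss (35-44%) if it is at month 3 only, to no power beyond the 5% error rate if it is at discharge only. In the month-1-only case, 35-44% of trials would be significant although both declared effects are zero.

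**What to change.** In E.5, for H1.1, H1.2, H2.1 and H3.1:

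1. Include discharge, month 1 and month 3 as occasions, with baseline, stratum, treatment and treatment-by-occasion terms. The planned sandwich variance can stay.
2. Name the treatment differences at discharge and at 3 months as the primary contrasts.
3. State whether alpha is shared between them. E.5 argues against adjustment across outcomes but wants to limit multiplicity across occasions, so this has to be said. Holm over the two is one option.
4. Make the month 1 and 3 average secondary.
5. State that the omnibus group-by-occasion interaction is not the test of these hypotheses.
6. State in Section 13.1 that the general time-by-treatment model is this model.

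Alternatively, if the sponsor prefers the average, change the declared primary outcome in the Synopsis and Section 2.2, and the aims, to match. Do this before any between-arm outcome comparison. Under either route, say why the mediation models use month 1 and Exploratory Aim 1 uses discharge and 3 months.

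**Cost.** No new data are needed. With two contrasts, the price is an 8-10% chance of at least one false positive per outcome if unadjusted. With Holm, first-step power is about 71-74% for the five outcomes checked, below the planned 80%, unless baseline adjustment recovers it (86% for caregiver distress at an assumed baseline correlation of 0.5). The primary test also gives up the average's advantage under a constant benefit.
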